- 128 predictability of the participants' clinical outcomes. In this application, we will evaluate the safety
- and feasibility of our CALEC product as well as its efficacy in treating the LSCD.
- 130

131 **2. STUDY AIMS**

132 The main aim of the study is to determine preliminary estimates of the safety and feasibility of

133 cultivated autologous limbal epithelial cell (CALEC) transplantation in the treatment of unilateral

LSCD. Secondarily, efficacy of CALEC will be investigated. This secondary objective is intendedto be exploratory rather than conclusive.

136

140

143

145

137 2.1. PRIMARY OBJECTIVES

- 138 1. **Safety:** To establish the safety of CALEC transplantation by determining the incidence of 139 primary ocular adverse events through 18 months of follow-up.
- 1411422. Feasibility: To establish feasibility of manufacturing CALEC for corneal surface reconstruction.

144 **2.2. SECONDARY OBJECTIVES**

- Efficacy: To investigate whether CALEC transplantation is efficacious in treatment of LSCD participants by comparing pre-operative to post-operative clinical parameters at months 3, 12, and 18.
- 149 150

151 2.3. STUDY CONCLUSIONS

152 The results of this Phase I/II study will provide guidance on whether to continue to a larger

153 Phase III study and will also provide preliminary data to help determine sample size for future

154 trials. Generally, if the study is not halted for feasibility issues, and there are no major safety or

155 efficacy concerns, a larger study of CALEC could be considered. However, caveats of the study

156 data and other potential factors outside of the trial will need to be considered and weighed in the

157 ultimate decision of whether to proceed.

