1185 9.3. STUDY HALTING GUIDELINES

- 1186 The DSMC may recommend at any time whether the study should continue per protocol, be
- 1187 further investigated, be discontinued, or be modified and then proceed. The FDA may also
- 1188 suspend additional enrollment and study interventions/administration of study product for the
- 1189 entire study, if applicable.
- 1190
- 1191 There will be no formal halting guidelines for safety, as the DSMC will receive full safety reports 1192 on Phase A participants as noted in Section 9.2 above, and will also expeditiously receive some 1193 events as noted in Section 9.2 above throughout the duration of the study.
- 1194 1195
- 1196 Halting guidelines for feasibility are as follows:

1197	•	A temporary suspension of enrollment will occur if four of the first eight CALEC biopsies,
1198		across Phases A and B, result in failure.
1199		• This could include two biopsies originating from one participant, (i.e., each biopsy
1200		would count separately)
1201		• Multiple construct attempts based on the same biopsy would be considered inclusive
1202		of a single biopsy
1203	٠	If this criterion is met, the DSMC will be notified expeditiously and enrollment activities will
1204		be temporarily suspended until further direction from the DSMC. Starting from the time the
1205		criteria are identified as met, until the time the DSMC provides further direction, the
1206		temporary suspension of enrollment activities will be defined as follows.
1207		 No participants will be consented
1208		• Participants who have consented and are in some stage of completing screening or
1209		baseline visits will be on hold (labs values that have already been processed may be
1210		collected and entered into the CRF)
1211		 Participants who have not completed a biopsy will be on hold
1212		 Participants who had already completed transplant and thus in follow up will not be
1213		on hold
1214		
1215		

1216 **10. MONITORING PROTOCOL ADHERENCE**

- 1217 Details for monitoring clinical site for protocol adherence can be found in the Monitoring Plan.
- 1218 The Clinical Center will oversee personnel training and certification, IRB approval and reporting,
- 1219 participant recruitment and retention. The day-to-day local clinical procedures monitoring will be
- 1220 performed by the Clinical Research Supervisor with the support of study website reports
- 1221 provided by the Coordinating Center. The monitoring will be conducted to ensure human

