4.0 Sample Size Considerations

The primary objectives of this study are to establish feasibility and to show safety of the CALEC transplantation by estimated the incidence of ocular adverse events (infection, corneal perforation, and/or graft detachment) through 18 months of follow-up. The secondary efficacy objectives are intended to be exploratory rather than conclusive. The efficacy results will provide preliminary data on potential effect size and variability, to help select sample size for future trials. No formal hypothesis testing comparing CALEC to CLAU is planned/ Sample size will not be based on a power calculation for a formal statistical comparison of CALEC to CLAU.

The sample size for Phase A will be 3 participants completing a CALEC transplant. The sample size for Phase B will be 21 participants randomized 2:1 using a block stratification (see protocol excerpt at the end of this section for details on randomization method), resulting in 13-15 CALEC participants and 6-8 CLAU participants. This process would ultimately yield a total of 24 participants (16-18 CALEC participants and 6-8 CLAU participants) across Phase A and B. About 5% of participants may withdraw from the study before reaching 18 months of follow-up (approximately 1 in each group). Thus, the total number of CALEC participants (Phase A and B) with complete follow up could be as few as 15. This minimum target of 15 CALEC participants is what was used to confirm that the sample size would be acceptable for the study, which is also supported by the analyses below which (1) describes the precision on safety rate estimates with 15 CALEC participants and (2) describes the ability to detect occurrence of the primary safety events of interest within a range around 15 CALEC participants.

(1) With a sample size of 15 in the CALEC group, the table below shows the 95% confidence interval for the percentage of participants with at least one primary safety event for varying potential observed results (the same table could apply to either a combined outcome or each type of event separately). For example, if 1 of 15 CALEC group participants experiences a graft detachment event in the study, the 95% confidence interval around the estimated percentage of patients that we expect would

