5.0 Statistical Analysis Plan

Safety Analysis

 Coding of all adverse events for analysis will be based on the MedDRA coding determined by the Medical Monitor. The following safety analyses will be performed.

1. Primary Safety Analysis (within-CALEC group evaluation of primary safety outcomes):

- a. The primary safety events of interest (ocular infection, corneal perforation, and graft detachment >=50%) in the recipient eye will be summarized as the numbers and percentages (and 95% exact confidence intervals) of participants having each event and the number and percentage (and 95% exact confidence intervals) of participants having any of the three events, up to 18 months.
 - These events will be evaluated in CALEC Group Phase A and Phase B participants combined. Only participants who completed transplant and only events occurring after transplant will be included.

2. Primary Safety Analysis (CALEC versus CLAU comparison of primary safety outcomes):

- a. The primary safety events of interest (ocular infection, corneal perforation, and graft detachment >=50%) in the recipient eye will be summarized as the numbers and percentages (and 95% exact confidence intervals) of participants having each event and the number and percentage (and 95% exact confidence intervals) or participants having any of the three events, up to 18 months
 - i. These events will be evaluated within each treatment group, in Phase B participants only. All participants who were randomized will be included regardless of whether transplant was completed. Phase B participants who discontinued prior to randomization will not be included. All events occurring after randomization will be included. Events prior to randomization will not be included.
- b. The two treatment groups will also be compared by computing the differences in percentages (and 95% exact confidence intervals) having each event and the difference in percentages (and 95% exact confidence intervals) having any of the three events.
- 3. Secondary Safety Analysis (explore/evaluate all adverse events): All reported adverse events up to 18 months (including systemic, recipient, and donor eye events) will be evaluated as follows.

- a. Within each MedDRA system organ class, tabulate the number and percentage of participants having at least 1 event within the given system organ class. Evaluate both of the following ways:

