 - b. Adverse Events designated by the DSMC as requiring expedited reporting (defined in the DSMC Charter) will be tabulated. The Charter describes in detail whether the events of interest are related to the donor or recipient eye and the time frame for classifying an event as an expedited event. CALEC Group Phase A, CALEC Group Phase B, and CLAU Group will be tabulated separately.
- Feasibility Analysis
- Feasibility will be assessed in the CALEC group only, using patients from both Phase A and Phase B. Each biopsy attempt will be classified as a "feasibility success" if it produced at least one construct that met all of the Quality Control (QC) release criteria in the CALEC Manual of Procedures. Secondarily, the number of biopsy attempts for each patient, as well as the QC results of all construct attempts for each biopsy, will be explored.
- The following feasibility analyses will be performed.

- 1. **Primary Feasibility Analysis:** On a biopsy level (denominator is the total number of biopsies performed)
 - o Number and percentage of biopsy attempts resulting in a feasibility success
- 2. Secondary Feasibility Analysis: On a patient level (denominator is all patients for whom at least 1 biopsy was performed)
 - o Categorize the number and percentage of patients for whom the biopsy (1) produced a feasibility success on the first biopsy attempt, (2) failed first attempt but produced a success on a second biopsy attempt, (3) failed 2 attempts, or (4) failed first attempt and a second was not attempted
- 3. Secondary Feasibility Analysis: On a construct level
 - o Categorize the number and percentage of constructs that met all QC release criteria
 - The QC criteria that failed and the data for each individual QC release criteria will also be explored.

Efficacy Analysis

The following efficacy analyses will be performed.

- 1. Primary Efficacy Analysis (within-CALEC evaluation of primary efficacy outcome):
 - a. The primary efficacy outcome measure is the binary outcome "Complete Success" of the graft versus not (as defined in the Protocol). This measure will be evaluated at each of the following three time points: 3, 12 and 18 months. The number and percentage of participants meeting the "Complete Success" criteria will be tabulated at each of these time points.
 - i. Evaluate in CALEC Group Phase A and Phase B participants combined. Only participants who completed transplant will be included.

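### Per-biopsy manufacturing success, a primary feasibility result, is planned as a bare percentage, while the primary safety proportions get exact 95% confidence intervals

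*SAP*

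**What the plan says.** Protocol 2.1 lists feasibility as the second primary objective: "To establish feasibility of manufacturing CALEC for corneal surface reconstruction". SAP 4.0 repeats the pairing: "The primary objectives of this study are to establish feasibility and to show safety of the CALEC" transplantation. The opening of Protocol 2 describes the main aim as obtaining preliminary estimates of both.

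The SAP then handles the two objectives differently.

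- **Safety.** In SAP 5.0, Primary Safety Analysis 1, the primary events "will be summarized as the numbers and percentages (and 95% exact confidence intervals) of participants having each event", and the same is specified for having any of the three events. SAP 4.0 supports this with an analysis that "describes the precision on safety rate estimates with 15 CALEC participants".
- **Feasibility.** In SAP 5.0, Primary Feasibility Analysis 1, the result is "Number and percentage of biopsy attempts resulting in a feasibility success". The denominator is all biopsies performed, and no interval is mentioned. Secondary Feasibility Analyses 2 (per patient, including success on the first attempt) and 3 (per construct) are also counts and percentages. SAP 4.0 gives no precision for feasibility.

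Three other provisions bear on the denominator. Protocol 5.5 ends enrollment at 17 CALEC transplants, or earlier if time for follow-up runs out. Protocol 5.6 allows a second biopsy, and only where the reason for failure is judged unlikely to recur. Protocol 15.7.2 limits the primary feasibility analysis to biopsies for initial transplants.

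**The concern.** When a trial sets out to estimate a proportion, the precision of the estimate is part of the result. The SAP accepts this for safety, where it uses exact intervals because the sample is small. It gives no reason for treating the other primary objective differently, so the difference looks like an omission.

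With around 20 biopsies, a success percentage in the high eighties can arise from a process that fails rarely or from one that fails in nearly a third of attempts. A bare percentage does not tell the reader which of these the data can rule out. That matters because Protocol 2.3 says of the findings: "The results of this Phase I/II study will provide guidance on whether to continue to a larger" Phase III trial. Whether the product can be made reliably is part of that question.

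**Working it through.** **1. Reproduce the plan's own precision figures.** The method is the exact (Clopper-Pearson) binomial interval. For x events in n, the lower limit is the 0.025 quantile of Beta(x, n − x + 1) and the upper limit is the 0.975 quantile of Beta(x + 1, n − x). For the SAP 4.0 safety table (n = 15):

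| Events | SAP 4.0 | Recomputed |
|---|---|---|
| 0 | 0 to 22% | 0 to 21.8% |
| 1 | 0 to 32% | 0.2 to 32.0% |
| 2 | 2 to 40% | 1.7 to 40.5% |
| 3 | 4 to 48% | 4.3 to 48.1% |
| 4 | 8 to 55% | 7.8 to 55.1% |
| 5 | 12 to 62% | 11.8 to 61.6% |

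The table reproduces, so the same method can be applied to feasibility.

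**2. Inputs for feasibility.** The documents give no biopsy total. I assume 17 successful biopsies, matching the transplant cap in Protocol 5.5, and 0 to 4 failures, so 17 to 21 biopsies. This is illustrative: enrollment may stop short of 17 transplants, and Protocol 7.1.2 counts a biopsy as a success even if surgery then does not take place for an unrelated reason.

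**3. Per-biopsy success.** For 17 of 19, the lower limit is the 0.025 quantile of Beta(17, 3) = 0.669 and the upper limit is the 0.975 quantile of Beta(18, 2) = 0.987.

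| Successes / biopsies | Success | Exact 95% CI |
|---|---|---|
| 17/17 | 100% | 80.5 to 100% |
| 17/18 | 94.4% | 72.7 to 99.9% |
| 17/19 | 89.5% | 66.9 to 98.7% |
| 17/20 | 85.0% | 62.1 to 96.8% |
| 17/21 | 81.0% | 58.1 to 94.6% |

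In terms of failure, 17/19 gives 10.5% with limits 100 − 98.7 = 1.3% and 100 − 66.9 = 33.1%. For 17/21 the failure limits are 5.4% and 41.9%.

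**4. First-attempt success, one biopsy per participant.** Two scenarios are consistent with the totals above:

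- 17 participants, 2 first failures, both repeated successfully. Per biopsy this is 17/19. First-attempt success is 15/17 = 88.2% (63.6 to 98.5%).
- 19 participants, 4 first failures, 2 repeated successfully. Per biopsy this is 17/21. First-attempt success is 15/19 = 78.9% (54.4 to 93.9%).

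**5. Does within-participant dependence spoil the interval?** The exact interval treats biopsies as independent, but a second biopsy comes from a participant whose first failed. This was checked by simulation (40,000 trials per setting). Enrollment ran to 17 transplants, first biopsies failed with probability 0.1 to 0.3, half or all failures were repeated, and a repeat failed with probability r.

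| Interval | r up to 0.5 | r = 0.8 | r = 1 |
|---|---|---|---|
| Per biopsy | 95.0 to 99.7% | 92.4 to 97.3% | 85.4 to 96.2% |
| First attempt | 96.3 to 98.9% in every setting | | |

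Entries are coverage. For the per-biopsy interval the target is the long-run failure proportion over all biopsies. That interval falls short only when repeats nearly always fail, which is what the Protocol 5.6 selection is meant to avoid. The first-attempt interval does not have the problem.

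**The case against.** The strongest reply is that little is lost. The numerator and denominator will be reported, and any reader can compute the interval from them. The aim is only preliminary estimation, and the within-CALEC primary efficacy analysis is also planned without an interval, so this may be the SAP's ordinary descriptive style for within-group results. Much of this stands: no estimate, population or data item is wrong, and the point is minor. It does not remove the gap. Efficacy is declared exploratory, while feasibility is a primary objective. The safety counts could be converted just as easily, yet the SAP specifies intervals for them. Specifying the interval in advance also settles which biopsies count and how repeats are handled.

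A second reply is that the biopsy totals are assumed. That is correct. But within the assumed range the interval is wide even in the best case, where 17/17 has a lower limit of 80.5%.

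A reader might also infer something stronger: that feasibility will be declared simply because the study was not stopped. Protocol 2.3 does say "Generally, if the study is not halted for feasibility issues, and there are no major safety or" efficacy concerns, a larger study could be considered, and Protocol 9.3 gives one numeric feasibility rule: "A temporary suspension of enrollment will occur if four of the first eight CALEC biopsies" fail. With independent biopsies, the chance of fewer than four failures in eight is 0.806 even at a 30% failure rate. The documents do not support the inference. Protocol 2.3 is hedged, says the results as a whole give guidance, and says caveats will be weighed. The rule triggers a temporary suspension pending DSMC direction, and the DSMC can recommend discontinuation at any time, so 0.806 is not the probability that the study is not halted. No document calls a 30% failure rate unacceptable.

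**Conclusion.** The point holds as a minor reporting gap. A primary result is planned without its precision, and the precision will be poor. Under the assumed 17 to 21 biopsies with 17 successes, the exact 95% interval spans about 20 percentage points (17/17: 100 − 80.5 = 19.5) to about 37 (17/21: 94.6 − 58.1 = 36.5). In the 17/19 example, failure in up to about one third of biopsies is not excluded.

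The conclusion that an interval is missing rests on the text alone. The widths rest on the assumed totals and on treating biopsies as independent. The simulation suggests independence is tolerable unless repeat biopsies almost always fail.

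A reader might go further and set the result against the 5-10% failure expectation in SAP 3.0, arguing that its unit (constructs) differs from the primary analysis (biopsies). No planned analysis or decision uses that expectation, and the documents do not fix how many constructs each biopsy yields, so no numerical conversion between the two can be defended. Nor does anything here show that the halting rule is inadequate or that Protocol 2.3 needs rewording.

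**What to change.** Make two additions to SAP 5.0, Feasibility Analysis.

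1. In Primary Feasibility Analysis 1, report an exact 95% confidence interval with the per-biopsy success percentage. State that only biopsies for initial transplants are included, in line with Protocol 15.7.2, and that the interval treats repeat biopsies in the same participant as independent.
2. In Secondary Feasibility Analysis 2, report an exact 95% confidence interval for the percentage of patients whose first biopsy attempt succeeded. This has one biopsy per participant and so avoids the independence problem.

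No new data are needed, and the halting guideline and trial conduct stay as they are. The cost is a short SAP edit and two computed intervals. The downside is presentational: with so few biopsies the intervals will be wide, and the feasibility result may look less favourable than the percentage alone.

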240 241 group interactions. 242 243 244 245 246 247 248 participants who completed transplant will be included. 249 ii. Missing data will not be imputed for this secondary analysis. 250 251 252 253 254 255 256 257 258 259 260 analysis as failures. 261 iii. Missing data will not be imputed for this secondary analysis. 262 263 264 265 266 267 268 269 where the data are collected. 270 271 272 continuous variable 273 274 assessment*) ≥75% 275 276 continuous variable 277 278 scale) by ≥50% 279 280 variable 281 282 7) Percentage change from baseline in OSDI score - continuous variable 283 8) Proportion of participants with decrease in OSDI score by ≥25% 284 9) Percentage change from baseline in SANDE score - continuous variable 285 10) Proportion of participants with decrease in SANDE score by ≥25% 286 * Epithelial defect surface area based on photographic images will also be evaluated. 287 288 289 290 percentages. 291 292

month) will be applied using a mixed effects logistic regression, including time by treatment

3. Secondary Efficacy Analysis (within-CALEC group evaluation of secondary efficacy outcome):

- a. The secondary efficacy outcome measure is the 3 level categorical outcome ("Complete Success", "Partial Success", "Not a Success", as defined in the Protocol). This measure will be evaluated at each of the following three time points: 3, 12 and 18 months. The number and percent of participants in each outcome category will be tabulated at each of these time points.
 - i. Evaluate in CALEC Group Phase A and Phase B participants combined. Only

4. Secondary Efficacy Analysis (CALEC versus CLAU comparison of secondary efficacy outcome):

- a. The secondary efficacy outcome measure is the 3 level categorical outcome ("Complete Success", "Partial Success", "Not a Success", as defined in the Protocol). This measure will be evaluated at each of the following three time points: 3, 12 and 18 months. The number and percent of participants in each outcome category will be tabulated at each of these time points.
 - i. Evaluate within each treatment group, in Phase B participants only. All participants who were randomized will be included regardless of whether transplant was completed. Phase B participants who discontinued prior to randomization will not be included.
 - ii. Participants who are randomized but do not receive a transplant will be included in the

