 - iv. Comparisons between CALEC and CLAU will be made between the two Phase B (randomized) groups only by computing the differences in percentages and 95% confidence intervals around those differences, at each time point.
- 5. Secondary Efficacy Analyses (explore the individual efficacy outcome measures that contributed to the primary and secondary composite outcome measures): Efficacy will be explored by evaluating each outcome listed below at each protocol-specific time point
 - 1) Percentage change from baseline in frank epithelial defect surface area (clinical assessment*) -
 - 2) Proportion of participants with decrease in frank epithelial defect surface area (clinical
 - 3) Percentage change from baseline in surface staining (clinical assessment, NEI grading scale) -
 - 4) Proportion of participants with decrease in surface staining (clinical assessment ,NEI grading
 - 5) Percentage change from baseline in neovascular area (photographic images) continuous
 - 6) Proportion of participants with decrease in neovascular area (photographic images) by ≥25%

Continuous efficacy variables will be summarized by sample size, mean, median, standard deviation, minimum and maximum. Discrete efficacy variables will be summarized by frequencies and

These summary statistics will be presented within each of the following:

293

94 6 **Witi** 95 Only

Within-CALEC group: Evaluate in CALEC Group Phase A and Phase B participants combined. Only participants who completed transplant will be included.

o *CALEC versus CLAU comparison*: Evaluate within each treatment group, in Phase B participants only. All randomized participants will be included regardless of whether the transplant was completed. Phase B participants who discontinued prior to randomization will not be included.

• Exact 95% confidence intervals for the difference between treatment groups in means for continuous variables and in proportions will be provided.

Missing data will not be imputed for this secondary analysis.

Additional Tabulations and Analyses

Baseline demographic and clinical characteristics will be tabulated according to treatment group. Continuous variables will be summarized by sample size, mean, median, standard deviation, minimum and maximum. Discrete variables will be summarized by frequencies and percentages

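### SAP 5.0 item 5 reports NEI staining, OSDI and SANDE as continuous outcomes only by percentage change, so a few low-baseline participants can distort the mean and make the SD unstable; add change in original units

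*SAP*

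**What the plan says.** Item 5 of the Efficacy Analysis in SAP 5.0 lists the components of the composite outcomes. Each has one continuous form and one responder proportion. The continuous forms that matter here are measure 3, "Percentage change from baseline in surface staining (clinical assessment, NEI grading scale"; measure 7, "Percentage change from baseline in OSDI score - continuous variable"; and measure 9, "Percentage change from baseline in SANDE score - continuous variable". Measure 5, neovascular area, has the same form.

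The summary rule is "Continuous efficacy variables will be summarized by sample size, mean, median, standard deviation, minimum and maximum". The one interval specified for continuous measures is for a between-group contrast: "Exact 95% confidence intervals for the difference between treatment groups in means for continuous variables".

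For these measures the SAP specifies no change in original units, no visit value and no baseline-adjusted model. The linear mixed models under Additional Tabulations and Analyses cover visual acuity, IOP, opacification and impression cytology only. Item 5 has no rule for a small or zero baseline.

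SAP 4.0 states what the efficacy data are for: "The efficacy results will provide preliminary data on potential effect size and variability, to help select sample size for future trials".

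**The concern.** Percentage change cannot go below -100%, has no comparable limit above, and takes its size from the individual baseline. A rise of a few points from a very low score can outweigh moderate falls in many other participants. Measurement error adds to this: a baseline that reads low by chance tends to be followed by a higher reading, and the small denominator magnifies the difference.

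Protocol 5.1 and 5.2 set no minimum OSDI, SANDE or staining score, so low baselines can occur. OSDI runs 0-100 (Protocol Appendix I), SANDE uses two 100 mm lines (6.6.1.2) and NEI staining runs 0-15 (Appendix II).

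At stake is the quality of two descriptive figures, the mean and the SD. The SD is the only variability figure that item 5 would hand to the planners of a later trial for these scores.

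**Working it through.** **The plan's own figures.** Item 5 states no effect size, SD or baseline distribution, so there is nothing to reproduce. The sample size comes from Protocol 5.5 (17 CALEC transplants) and SAP 4.0 (a minimum of 15). All other inputs below are assumptions.

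**Step 1: five-person example.** Baselines 60, 50, 40, 30, 10; follow-up 40, 35, 30, 25, 30.
- Absolute changes: -20, -15, -10, -5, +20. Mean -6 (38 to 32), SD 15.6.
- Percentage changes: -33.3, -30, -25, -16.7, +200. Mean = 95/5 = +19%, SD 101. Median -25%.

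**Step 2: fifteen-person example.** Thirteen participants with baselines from 35 to 70 (sum 670) all fall by 30%. Two, at 4.17 and 2.08, each rise 6.25 points, that is +150% and +300%.
- Mean percentage change = (13 × (-30) + 150 + 300)/15 = 60/15 = +4.0%, SD 94.
- Mean absolute change = (-0.30 × 670 + 12.5)/15 = -188.5/15 = -12.6, SD 8.2.
- The median percentage change is -30%, and 13/15 = 87% are responders at the 25% cut-off.

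**Step 3: break-even.** If 15 - k participants fall by 30%, the other k bring the mean to zero when each rises by (15 - k) × 30/k percent: 420% for k = 1, 195% for k = 2, 120% for k = 3. Two participants at NEI 1 need only reach about 3 (1 × 2.95). From a baseline of 20, one participant would need 20 × 5.2 = 104, which a 0-100 scale does not allow. The sign effect is therefore mainly a near-floor effect.

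**Step 4: simulation.** n = 17; baseline mean 45, SD 22, limited to the range from the stated floor to 100; independent measurement error with SD 8 or 12 at both visits.

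| Baseline floor | True fall | Mean percentage change has wrong sign (SD 8 to SD 12) |
|---|---|---|
| 4 | 20% | 12% to 32% |
| 4 | 30% | 4% to 18% |
| 4 | 40% | 1% to 8% |
| 10 | 30% | 0.2% to 4% |
| 20 | 20% | 0.3% to 5% |
| 20 | 30% | 0% to 0.4% |

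At floor 4 and a 20% fall, mean absolute change has the wrong sign in 0.1% to 1.1% of trials, and the median percentage change in 0.4% to 3.6%. With no true change, the mean percentage change averages +8% to +18%.

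The 5th to 95th percentiles of the SD in that case are:
- percentage change: 19 to 96 (measurement SD 8) and 28 to 177 (measurement SD 12), a ratio of about 5 to 6;
- absolute change: 8.4 to 15.1 and 12.0 to 21.7, a ratio of about 1.8.

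Sample size for a given difference scales with SD squared. The spread in planned size is then roughly 25-fold (96/19, squared) to 40-fold (177/28, squared), against about 3-fold (1.8²).

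**Step 5: milder model.** n = 15, with a fixed 10-point fall applied to the recorded baseline, so that low scores do not drift back up. For OSDI with mean 30 to 40, SD 20 to 25 and a floor of about 2, the sign reverses in 3% to 6% of trials and the SD-squared spread is 10 to 21, against 3.6 to 3.7 for absolute change. For NEI staining (mean 6, SD 4, 1.5-point fall) the figures are 1%, and 6.6 against 3.8. With OSDI kept at 20 or more, or NEI at 4 or more, reversal is 0% and the spread is 4.5 to 5.0 against 3.5 to 3.6.

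**The case against.** Several points on the other side stand.

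- **The table is not mean and SD alone.** Median, minimum, maximum and a responder proportion are also planned. In the five-person example the median is -25%, 3 of 5 are responders and the maximum shows the +200% outlier. A careful reader would not mistake the direction.
- **The size depends on assumptions.** The documents give no baseline distribution or measurement error. The 20% fall is smaller than the 25% cut-off the plan uses for symptom improvement, and larger falls or higher baselines shrink the sign problem sharply.
- **Neovascular area is different.** Eligibility requires pannus beyond 2 mm over at least 6 clock hours, so a near-zero baseline is unlikely. The area is recorded in pixels (Protocol 6.6.7.1, Appendix III) and is not described as normalised, so relative change is a reasonable choice there.
- **The stakes are low.** Efficacy is exploratory, its primary outcome is binary, no test or decision uses mean percentage change, and a percentage metric matches the protocol's definitions of improvement.

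What the objection does not answer is the SD. The median, range and responder proportions do not supply one, and the SD of percentage change was less stable than that of absolute change in every scenario examined.

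**Conclusion.** The point holds as a low-cost improvement for NEI staining, OSDI and SANDE. Where low baselines occur, the mean percentage change is pulled toward worsening and sometimes has the wrong sign: about 12% to 32% of trials under the least favourable inputs examined, 0% to 5% with baselines floored at 20. The more consistent defect is the unstable SD. All of these sizes rest on assumed baselines, effects and measurement error.

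A reader might infer more than the documents support:
- **That sign reversal is the expected result.** It needs near-floor baselines, and the planned median and responder proportions would show the true direction.
- **That the trial's data would be unusable for planning.** The raw scores are collected, so absolute SDs can be derived later, and the variability of the binary primary efficacy outcome follows from its proportion.
- **That neovascular area needs the same remedy.** Its eligibility rule and its pixel unit argue against that.

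No study conclusion depends on item 5.

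**What to change.** In SAP 5.0 item 5:

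1. For NEI staining, OSDI and SANDE, add change from baseline in original units (mean, SD, 95% CI, median, range) as the main continuous summary.
2. For the same three scores, show percentage change by median and range only.
3. Keep percentage change for neovascular area. Optionally add the change in the fraction of the delineated corneal area, since the measurement procedure already delineates a total area.
4. Leave the responder proportions and their cut-offs unchanged.

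No new data are needed. The cost is SAP wording and a few extra table rows. Making the change before the results are seen also avoids choosing the metric afterwards.
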